11.1. General Statistical Considerations

Patients treated with the same dose level and schedule will be pooled into a single treatment group. All statistical analyses will be performed by treatment group, unless otherwise noted. Subjects whose dose is reduced will be analyzed in the dose group before dose reduction.

Baseline values of each subject, unless otherwise specified, will be the last observed values that are available before the first dose of the study drug.

Unless otherwise noted, continuous variables will be summarized by the number of subjects analyzed, arithmetic mean, standard deviation, minimum, median, and maximum, whereas categorical variables will be summarized by frequency and proportion.

Analyses of changes from baseline (eg, absolute change, shift table) will be performed for subjects with the baseline value and at least one value available after treatment. Two-sided 95% confidence interval (CI) will be determined, unless otherwise noted.

11.2. Analysis Sets

The sponsor will define the criteria for inclusion of subjects in each analysis set in the Statistical Analysis Plan, and will determine whether each subject should be included or not according to the criteria. Subjects with major Good Clinical Practice (GCP) violations (eg, a violation of informed consent procedure, a major violation of study procedures) will be excluded from all analysis sets.

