5.3.2. Definition of Maximum Tolerated Dose

If any of the following completion criteria are met, the MTD will be determined based on comprehensive evaluation of the recommended dose guided by mCRM incorporating the EWOC principle, and safety and PK/PDy information of DS-3032b.

Completion criteria:

- DLT evaluation is completed in at least 15 subjects in the entire study and in at least 6 subjects in the cohort of the dose selected to be the dose for the next cohort by mCRM.
- DLT evaluation is completed in at least 6 subjects in the cohort of the dose selected to be the dose for the next cohort by mCRM, with at least 50% posterior probability for the DLT rate ranging between 16% and 33%.
- DLT evaluation is completed in at least 3 subjects in the cohort of each dose, with no DLTs reported.
- The posterior probability for the DLT rate of 33% or higher in the 90 mg cohort is at least 60%.

5.3.3. Study Treatment to Subjects in Each Cohort and Procedure for Proceeding to the Next Cohort

In the cohort of the first dose, study treatment for the second subject must be started after an at least 1-week interval from the first dose of treatment in the first subject. In the subsequent cohorts, study treatment for the next subject may be started on the following day of the start day of study treatment in the first subject.

If proceeding to the next cohort involves an increase in the dose, study treatment for the first subject in the new cohort will be started after the end of the DLT evaluation period in at least 3 subjects in the ongoing cohort. If a DLT occurs in 2 subjects before registration of the third subject, the dose for the third subject will be reviewed by using the mCRM incorporating the EWOC principle.

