11.2.1. Safety Analysis Set

The safety analysis set will include subjects enrolled in the study but will exclude “subjects who have not received any dose of the study drug.”

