11.2.2. Maximum Tolerated Dose Analysis Set

The MTD analysis set will include all subjects who received at least one dose of the study drug but will exclude subjects who have missing data of one or more examination or observation items during the DLT evaluation period for other reasons than adverse drug reactions (worsening of clinical conditions due to progression of the primary disease, AEs for which a relationship with the study drug is ruled out, etc.) and whose DLT evaluation could not be performed appropriately. The MTD analysis set will also include subjects who have experienced DLT in Cycle 1 and subjects who have received the study drug on at least 75% of the specified days in Cycle 1 in the absence of DLT.

Subjects for whom the study treatment is postponed due to a DLT occurring during the DLT evaluation period, and the study treatment is then resumed at a reduced dose will be

handled as those included in the MTD analysis set for the dose level at the first dose of the study drug.

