11.3. Data Handling

The sponsor will decide the handling of individual data in consultation with the medical expert as needed, and lock data.

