11.4.2. Safety Analysis

Safety will be analyzed in the safety analysis set, unless otherwise noted. AEs that occur or worsen relative to the pre-treatment state after the start of study treatment (TEAEs) will be tabulated. AE terms will be converted using the Medical Dictionary for Regulatory Activities (MedDRA) terminology developed by the ICH. Individual AEs will be grouped by organ system using the system organ classes (SOC) of MedDRA, and be summarized in the preferred term (PT) level.

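### Section 11.2 drops dosed subjects with a major GCP violation from every analysis set, including the safety and MTD sets

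*Combined protocol and SAP*

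**What the plan says.** Section 11.2 sets a rule ahead of the individual set definitions. Subjects with major GCP violations, for example "a violation of informed consent procedure, a major violation of study procedures) will be excluded from all analysis sets". It makes no exception for subjects who were dosed or who had a DLT. The same section says that the sponsor will define inclusion criteria in the separate SAP and determine each subject's inclusion from them.

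The set definitions read differently:

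- Section 11.2.1: "The safety analysis set will include subjects enrolled in the study but will exclude" those who never received a dose. It names no other exclusion.
- Section 11.2.2: "The MTD analysis set will also include subjects who have experienced DLT in Cycle 1".
- Section 11.4.2: "Safety will be analyzed in the safety analysis set, unless otherwise noted". The TEAE tables therefore follow the safety set.
- Section 11.3: "The sponsor will decide the handling of individual data in consultation with the medical expert as needed, and lock data".

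On the MTD, section 5.3.2 says that, once a completion criterion is met, "the MTD will be determined based on comprehensive evaluation of the recommended dose guided by mCRM", together with safety and PK/PDy information.

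For efficacy, sections 11.2.3 and 11.4.3 calculate the CRc, response and transplantation rates only in treated subjects with at least one post-dose efficacy evaluation. Table 10.1.1 has an Unknown category for subjects without one, but the best-response list in 11.4.3 does not carry it.

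**The concern.** Safety, tolerability and the MTD are the primary objective. A procedural violation does not undo exposure: a subject who took the drug and had a toxicity still informs its safety. If 11.2 governs, that subject's events leave the TEAE tables, and a Cycle 1 DLT leaves the MTD set.

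The decision is also exposed to knowledge of outcomes. There is no blinding, the sponsor determines membership, and the text does not say when membership is fixed or which procedural violations are major. With cohorts of 3 to 6, one DLT more or less can cross a decision threshold.

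The efficacy denominator is a separate and minor matter. Leaving out treated but unevaluated subjects raises the CRc and response rates if those subjects are non-responders. The transplantation rate needs no response evaluation, yet it is conditioned on one.

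**Working it through.** **Step 1: the text.** Take a dosed subject with a major procedural violation and a Cycle 1 DLT.

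| Section | Safety set | MTD set |
|---|---|---|
| 11.2 | out | out |
| 11.2.1 | in | not addressed |
| 11.2.2 | not addressed | in |

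As the opening rule, and with its reference to all sets, 11.2 most naturally prevails. The subject is then out of both.

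**Step 2: reproduce the plan's model.** Section 11.7.1 gives logit π(d) = log α + β·log(d/160). Section 11.7.2 gives (log α, log β) as bivariate normal with means (−1.8999, 1.3484), SDs (2.2792, 1.3727) and correlation −0.3157. At 160 mg the log-dose term is zero, so the prior median is 1/(1 + e^1.8999) = 13.0%. Numerical integration gives 3.1% at 120 mg. The plan states 13% and 3%, so the model is reproduced.

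**Step 3: decision rule.** The posterior is proportional to the prior times the product over doses of π^x(1−π)^(n−x), for x DLTs in n subjects, integrated on a 3001 × 3001 grid. I read the 25% in 11.7.3 as an upper limit on P(π > 33%). Among doses within the limit, the one with the highest probability of the 16–33% interval is chosen. The DLT counts are illustrative, as the plan contains no data.

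| DLTs at 90 / 120 / 160 mg | P(16–33%) at 120, 160 mg | P(>33%) at 120, 160 mg | Chosen |
|---|---|---|---|
| 0/3, 1/6, 2/6 | 32.2%, 47.3% | 4.1%, 35.3% | 120 mg |
| 0/3, 1/6, 1/5 (one DLT subject excluded) | 21.6%, 44.0% | 1.8%, 18.0% | 160 mg |
| 0/3, 0/6, 2/6 | – | 23.4% at 160 mg | 160 mg |
| 0/3, 0/6, 1/5 | – | 8.0% at 160 mg | 160 mg |
| 0/3, 2/6, 2/6 | – | 52.4% at 160 mg | 120 mg |
| 0/3, 2/6, 1/5 | – | 34.5% at 160 mg | 120 mg |

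The first row has 3 + 6 + 6 = 15 evaluated subjects and 6 at the chosen dose. It therefore meets the first completion criterion, which asks that "DLT evaluation is completed in at least 15 subjects in the entire study" and in at least 6 at the selected dose. The last four rows are two pairs in which the same exclusion changes nothing.

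**Step 4: the 90 mg completion criterion.** Section 5.3.2 also ends dose finding if P(π ≥ 33%) at 90 mg is at least 60%. With 2/3 DLTs the probability is 76.2%, and the criterion is met. With one DLT subject excluded (1/2) it is 46.9%, and it is not met. This alone would not permit escalation: under 5.3.3 a cohort at a higher dose "will be started after the end of the DLT evaluation period in at least 3 subjects in the ongoing cohort".

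**Step 5: how often.** Consider paths that complete under the first or second criterion with at least one DLT, and drop one randomly chosen DLT subject. Five sets of true DLT rates at 90/120/160 mg were assumed: 1/3/13, 3/10/25, 5/15/30, 10/20/35 and 5/20/40%.

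- Overdose limit at every step, second cohort held at 120 mg, target dose needing at least 6 treated: the choice moves up in 4.2, 10.3, 13.4, 16.4 and 16.1% of cases.
- Overdose limit from the third cohort, as 11.7.3 says, and a completion criterion still required among the subjects left in the analysis: about 2.0, 3.0, 3.6, 5.1 and 4.4%.

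**Step 6: efficacy denominator.** With one responder among 6 treated, the rate is 1/6 = 16.7% (Clopper–Pearson 95% CI 0.4–64.1). If one of the six is unevaluated, it becomes 1/5 = 20.0% (0.5–71.6), a factor of 6/5 = 1.20.

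**The case against.** Several points on the other side stand.

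- **Precedence.** A reader might infer that 11.2 and 11.2.2 contradict each other outright. The documents do not support that strongly. A rule on all sets, placed before the definitions, reads as a parent rule, and the sentence in 11.2.2 deals with evaluability rather than GCP validity. This settles which rule governs. It does not remove the effect, because under that reading the dosed subject is out.
- **The SAP.** Criteria are deferred to a separately prepared SAP whose text is not in the combined document. It may fix timing and define which violations are major. It would still have to depart from the protocol to keep these subjects.
- **The model runs.** Nothing ties the cohort-by-cohort runs to the 11.2 sets. The synopsis refers to all evaluable subjects, and 11.7.3 to the results of DLT evaluation. The figures in Steps 3 to 5 hold only if the exclusion is applied to the model data.
- **The safety record.** A reader might infer that toxicity would be concealed. It would not: AEs are still recorded (9.3), SAEs are still reported within 24 hours (9.5.2), and the MTD decision draws on all safety information.
- **The first example.** After 0/3 at 90 mg the rule alone favours 160 mg: target-interval probability is about 16% against 8% at 120 mg, P(>33%) is about 17%, and 160/90 = 1.78 is within the 2-fold limit. The example therefore assumes a 120 mg second cohort, as in the illustration in 11.6. After the exclusion, 14 analysed subjects remain, 5 of them at 160 mg, so it also assumes that completion is judged before the exclusion.
- **Efficacy.** An evaluable set is a declared choice for an exploratory objective.

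**Conclusion.** The point holds as a cheap improvement. The certain part is textual: as written, 11.2 removes dosed subjects with a major procedural violation from the safety tables and the MTD set, and in an open-label study the text leaves room to decide this with outcomes known.

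The numerical part is conditional. If the exclusion reaches the model, one removed DLT can cross the 25% limit (about 35% to 18% at 160 mg) or undo the 60% criterion (76% to 47% at 90 mg). Most exclusions change nothing. Across the assumed rates, an upward shift follows in roughly 2–5% or 4–16% of cases, depending on the counting rule, and only when a DLT and a major violation fall on the same subject. The documents do not say how often that happens. It would go too far to infer that the plan is likely to produce too high an MTD.

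The efficacy denominator is minor and adds nothing to the weight of the point.

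**What to change.** In 11.2, limit the exclusion from all sets to consent violations. Keep every other dosed subject in the safety set, with the violation flagged. Keep subjects with a Cycle 1 DLT in the MTD set unless the violation means that the DLT cannot be attributed to the assigned dose level; list those cases and run the BLRM with and without them. State that the same rule governs the cohort-by-cohort runs, and when set membership is fixed.

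As a secondary change, report the CRc, response and transplantation rates over all treated subjects next to the evaluable set, counting Unknown as non-response for CRc and response.

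The cost is a short protocol amendment with matching SAP wording, the added efficacy rates and a sensitivity run only if such a case arises. No new data are needed. The downside is that the safety tables will contain flagged subjects whose data may be less reliable, and the efficacy rates may be slightly lower.

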11.2.1. Safety Analysis Set

The safety analysis set will include subjects enrolled in the study but will exclude “subjects who have not received any dose of the study drug.”

11.2.2. Maximum Tolerated Dose Analysis Set

The MTD analysis set will include all subjects who received at least one dose of the study drug but will exclude subjects who have missing data of one or more examination or observation items during the DLT evaluation period for other reasons than adverse drug reactions (worsening of clinical conditions due to progression of the primary disease, AEs for which a relationship with the study drug is ruled out, etc.) and whose DLT evaluation could not be performed appropriately. The MTD analysis set will also include subjects who have experienced DLT in Cycle 1 and subjects who have received the study drug on at least 75% of the specified days in Cycle 1 in the absence of DLT.

Subjects for whom the study treatment is postponed due to a DLT occurring during the DLT evaluation period, and the study treatment is then resumed at a reduced dose will be

handled as those included in the MTD analysis set for the dose level at the first dose of the study drug.

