5.3. Definition of Dose-limiting Toxicities and Maximum Tolerated Dose

5.3.1. Definition of Dose-limiting Toxicities

A DLT is defined as any Grade 3 or higher non-hematological AE unless related to the primary disease, course of the primary disease, complications, or concomitant medications, that occurs during the DLT evaluation period (28 days of Cycle 1), with the exceptions as defined below:

1. The following events will be assessed as DLTs:
 - Grade 4 aspartate aminotransferase (AST)/alanine aminotransferase (ALT)

- Grade 3 AST/ALT lasting ≥ 3 days, Grade 3 AST/ALT with Grade ≥ 2 total bilirubin
- Unable to complete at least 75% of the prescribed doses of DS-3032b in Cycle 1 (28 days) as a result of Grade ≥ 2 events

2. The following events will not be assessed as DLTs:

- Grade 3 fatigue lasting < 3 days
- Grade 3 nausea or vomiting that has resolved to Grade ≤ 2 within 48 hours after antiemetic therapy
- Grade 3 diarrhea that has resolved to Grade ≤ 2 within 48 hours after antidiarrheal therapy
- Alopecia
- Febrile neutropenia
- Transient laboratory abnormalities that do not involve clinical symptoms and do not require continuous treatment (\geq Grade 3 ALP, uric acid, amylase, and lipase, hyponatremia that has resolved within 72 hours after onset, etc.)

The following hematological toxicities will be assessed as DLTs.

- Failure to recover neutrophil count to $\geq 500 /mm^3$ and platelet count to $\geq 20,000 /mm^3$, leading to a delay in starting Cycle 2 for more than 2 weeks

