5.5. Actions to be Taken for Adverse Events

If a toxicity that falls under the following definition occurs, dose interruption, postponement of the start of the next cycle (hereinafter, postponement), or dose reduction should be performed as shown below.

5.5.1. Occurrence of Dose-limiting Toxicities or Toxicities Equivalent to the Definition of Dose-limiting Toxicities after Cycle 1

If a DLT occurs or a treatment-related toxicity falling under the definition of DLTs occurs after Cycle 1, the investigator or subinvestigator should interrupt, postpone, or discontinue the study treatment. If the toxicity improves to Grade ≤ 1 or the subject recovers to the baseline condition, the investigator or subinvestigator will consider resuming the study treatment at a one-level reduced dose from the dose used in his/her participating cohort (in the case of the 90 mg cohort, resumption at a dose of 90 mg should be considered), only when it is considered beneficial to the subject. Once the dose is reduced, the dose should not be increased again.

The duration of dose interruption must not exceed 4 weeks. If the subject does not recover 4 weeks or more after the onset of the toxicity, the subject should be withdrawn from the study. In case a Grade ≥ 3 toxicity or a serious adverse event (SAE) that is apparently attributable to the primary disease occurs, the study treatment may be interrupted or postponed until the toxicity or the event improves to Grade ≤ 1 or until the subject recovers to the baseline condition.

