5.5.2. Occurrence of the Following Toxicities Not Listed in Section 5.5.1

If any of the following toxicities, not listed in “Section 5.5.1 Occurrence of Dose-limiting Toxicities or Toxicities Equivalent to the Definition of Dose-limiting Toxicities after Cycle 1,” occur, the investigator or subinvestigator will continue the study treatment if the toxicity can be controlled by appropriate intervention.

- Grade ≥ 2 non-hematological toxicity (excluding alopecia) unrelated to the primary disease, Grade ≥ 3 fatigue lasting >48 hours
- Grade ≥ 2 laboratory abnormalities not falling under the definition of DLTs
- Hypoplastic marrow (neutrophil count $<500 /mm^3$ and platelet count $<20,000 /mm^3$)

When it is considered necessary to interrupt or postpone the study treatment, interruption or postponement of the study treatment until the toxicity resolves to the following conditions will be considered. Resumption of the study treatment may be considered if the toxicity is confirmed to have improved or resolved within 4 weeks. When the study treatment is resumed, a reduction to the dose in the cohort that is one-level lower than the dose the pertinent subject was receiving before experiencing the toxicity will be considered.

- Neutrophil count $\geq 500 /mm^3$
- Platelet count $\geq 20,000 /mm^3$
- Grade ≥ 2 non-hematological toxicities (excluding alopecia) that have improved to Grade ≤ 1 or have resolved to baseline levels

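### A Cycle 1 dose reduction for non-DLT toxicity can leave a subject in the MTD analysis as DLT-free at the full cohort dose, because the 75% rule in Section 11.2.2 counts days and ignores dose

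*Combined protocol and SAP*

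**What the plan says.** Four provisions of the protocol meet here.

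- **Dose reduction.** Section 5.5.1 applies "If a DLT occurs or a treatment-related toxicity falling under the definition of DLTs occurs after Cycle 1". Section 5.5.2 takes the toxicities outside 5.5.1, among them Grade 2 or higher "non-hematological toxicity (excluding alopecia) unrelated to the primary disease". If treatment is interrupted and then resumed, the investigator considers "a reduction to the dose in the cohort that is one-level lower than the dose the pertinent subject was receiving before experiencing the toxicity". No cycle is named.
- **DLT definition.** No item in Section 5.3.1 mentions dose reduction. The nearest is "Unable to complete at least 75% of the prescribed doses of DS-3032b in Cycle 1 (28 days") because of Grade 2 or higher events.
- **MTD analysis set.** Section 11.2.2 includes "subjects who have received the study drug on at least 75% of the specified days in Cycle 1 in the absence of DLT". Its only paragraph on reduced doses concerns "Subjects for whom the study treatment is postponed due to a DLT occurring during the DLT evaluation period".
- **Dose group.** Section 11.1 states: "Subjects whose dose is reduced will be analyzed in the dose group before dose reduction".

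Section 5.6 also has a 75% withdrawal rule, counted in dosing days.

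**The concern.** Because 5.5.1 is confined to DLTs and their equivalents after Cycle 1, a non-DLT toxicity during Cycle 1 falls under 5.5.2, where stepping down a level is allowed. Such a subject has no DLT under any item that names the event, can satisfy the day count in 11.2.2 with days at the lower dose, and is analysed at the starting dose. The model then reads the subject as one complete observation that the cohort dose was tolerated for a cycle.

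The reduced-dose case that 11.2.2 does cover, reduction after a DLT, is harmless to the estimate: that subject already counts as a DLT at the starting dose. The case that can distort the estimate is not addressed. Assessing the MTD is part of the primary objective and cohorts are normally 3 to 6 subjects, so one misread subject carries weight.

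**Working it through.** **Inputs.** 14 dosing days per cycle in Subtrial A (5.2.2). Planned doses 90, 120 and 160 mg, and a 25% limit on the posterior probability that the DLT rate exceeds 33%, applied from the third cohort (11.7.3). Model: logit π(d) = log α + β log(d/160) (11.7.1). Prior on (log α, log β): means (−1.8999, 1.3484), SDs (2.2792, 1.3727), correlation −0.3157 (11.7.2). The text on the 25% gives no inequality; I read it as an upper limit.

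**Reproducing the plan's own figures.** At 160 mg the dose term is zero, so the prior median is 1/(1 + e^1.8999) = 13.0%. Numerical integration of the prior gives 3.05% at 120 mg. The plan states 13% and 3%, so the model is set up as intended.

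**What the day count lets through.** 0.75 × 14 = 10.5, so 11 days suffice and up to 3 may be missed.

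- *Case 1:* 1 day at 160 mg, 3 missed, 10 at 120 mg. Days: 11/14 = 78.6%. Dose: 160 + 10 × 120 = 1,360 mg of 14 × 160 = 2,240 mg, or 60.7%. From 120 to 90 mg: 120 + 10 × 90 = 1,020 of 1,680 mg, also 60.7%.
- *Case 2:* 7 days at 160 mg, 1 missed, 6 at 120 mg. Days: 13/14 = 92.9%. Dose: 7 × 160 + 6 × 120 = 1,840 of 2,240 mg, or 82.1%.

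Both pass 11.2.2. Whether Case 1 is already a DLT depends on how "75% of the prescribed doses of DS-3032b in Cycle 1 (28 days) as a result of Grade" is read. Counted in doses or days, it is not; counted in mg, 60.7% falls short and it is. Case 2 passes on either reading, although only 7 of 14 days (50%) were at the cohort dose.

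**What one subject is worth in the model.** Outcomes below are assumed: 0/3 at 90 mg and 0/3 at 120 mg throughout. Posterior probabilities for the DLT rate at 160 mg, by integration over the stated prior with a binomial likelihood:

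| DLTs at 160 mg | ≤16% | 16–33% | >33% |
|---|---|---|---|
| 0/3 | 0.89 | 0.09 | 0.02 |
| 1/3 | 0.47 | 0.32 | 0.21 |
| 2/3 | 0.12 | 0.28 | 0.60 |
| 1/6 | 0.67 | 0.26 | 0.07 |
| 2/6 | 0.31 | 0.42 | 0.26 |

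At 1/3, 160 mg is inside the 25% limit and has the highest target-interval probability (0.32, against 0.09 at 120 mg), so it is the recommended dose. At 2/3 it is excluded. At six subjects, the second DLT takes the probability from 0.07 to 0.26, just over the limit.

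At 120 mg (0/3 at 90 mg, nothing yet at 160 mg), moving from 0/3 to 1/3 takes the same probability for 160 mg from 0.115 to 0.441. With the subject not evaluable (0/2) it is 0.128.

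**Completion without a DLT.** One criterion in 5.3.2 needs at least 3 evaluated subjects at each dose and no DLTs, which Section 11.6 puts at 9 subjects. A stepped-down subject at 160 mg can be one of those nine. Counted as a DLT (1/3), the subject closes that route; counted as not evaluable (0/2), the subject leaves it unmet until replaced.

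**The case against.** Several counter-arguments have force.

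- *Unit of the 75%.* If the DLT item in 5.3.1 means mg, the 61% example is already a DLT. This stands, and limits Case 1 to one reading. Case 2 does not depend on it. Section 5.6, and the description of an earlier study's DLT in Section 1.3.1, use dosing days, which shows that the unit is unsettled.
- *Not-evaluable comparison.* A reader might infer that dropping the subject (1/2 at 160 mg, probability 0.31) would itself rule out 160 mg. It normally would not: the model is run after three evaluated subjects in principle, so a replacement comes first, and a DLT-free replacement returns the data to 1/3 and 0.21.
- *An MTD set too high.* A reader might infer that this will happen. The documents do not show it. The 6-subject illustrations contain 12 subjects, below the 15 of the first criterion in 5.3.2, and their target-interval probabilities (0.26 and 0.42) are below the 50% of the second. What is shown is a change in dose eligibility, plus exposure of the no-DLT completion route.
- *Frequency.* Nausea was reported in 68% to 76% of subjects in the earlier studies, and a reader might infer that such reductions will be common. Those are any-grade rates over the whole of treatment, largely on longer schedules. Section 5.5.2 favours continuing when the toxicity can be controlled; recovery must come within three missed doses for the day count to be met; and no planned level lies below 90 mg.
- *Other safeguards.* The model only guides, the MTD rests on a comprehensive evaluation, and Section 11.2 leaves detailed set criteria to a separate Statistical Analysis Plan. But 11.2.2 already states an operative rule, and clinical judgement does not correct what is entered in the model.

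Analysing by starting dose is a defensible choice and is not the complaint.

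**Conclusion.** The concern holds as a gap between sections. As written, a subject at 120 or 160 mg who resumes at a lower level within the Cycle 1 dosing days can be a full non-DLT at the cohort dose: with 61% of planned mg if the 5.3.1 item counts doses or days, and with 82% on either reading. The direction is toward understating the DLT rate.

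The size rests on assumed outcomes and on the 25% being an upper limit. One reclassified subject can carry 160 mg across that limit (0.21 to 0.60, or 0.07 to 0.26), but not in every configuration: 0/3 to 1/3 at 160 mg stays within it (0.02 to 0.21). These figures do not say which classification is right. That 5.5.2 reaches Cycle 1 is inferred from the absence of a restriction. I would rate this should-fix.

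**What to change.** - In 11.2.2, count the 75% for DLT-free subjects only on days at the assigned cohort dose level. State that a DLT-free subject below this is not evaluable for the MTD set. This needs to be an explicit exclusion, because the section's opening sentence otherwise admits every dosed subject whose Cycle 1 examinations are complete.
- Replace such a subject under 5.4, naming the case there: the automatic provision covers only withdrawal before the end of Cycle 1, and this subject may remain on treatment.
- Leave the second paragraph of 11.2.2 limited to reductions after a DLT. It includes subjects at their first dose level, so extending it would bring back those just excluded.
- Reconcile 5.3.1, 5.5.2, 5.6 and 11.2.2 on whether the 75% is in doses, days or mg, and on whether reduced-dose days count. Whether a toxicity-driven Cycle 1 reduction is a DLT is for the sponsor to decide.

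The cost is wording and an occasional replacement subject; Section 6.3 already records the daily dose in mg and any reduction. One limit remains: if such reductions are not classed as DLTs, replacing these subjects removes the false non-DLT but does not put their toxicity into the model. They should therefore be listed for each dose decision.

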5.4. Enrollment of Additional Subjects

If there is a subject who cannot be evaluated for DLTs because of withdrawal from the study before the end of Cycle 1 for any reason during the study, additional subjects will be enrolled. In other cases where enrollment of additional subjects is considered necessary, whether or not to enroll additional subjects will be considered through discussion between the investigator and the sponsor. The medical expert may join the discussion as necessary.

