6. STUDY PROCEDURES

6.1. List of Study Procedures

Study procedures specified in the protocol are shown in "[Appendix 1](#)."

In the study, the period from the day of informed consent through the end day of the Follow-up is defined as the "study period" for each subject. However, if follow-up of a subject at the study center becomes difficult for such reasons as transfer to another hospital or that the subject refuses to visit the site after the last dose of DS-3032b then the study duration for the pertinent subject will be terminated on the relevant day.

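### Section 11.2.2 gives two conflicting rules for a DLT-free subject who leaves Cycle 1 early; read literally, one counts partial observation as a full non-DLT

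*Combined protocol and SAP*

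**What the plan says.** - **DLT window (5.3.1).** A non-hematological DLT is a qualifying event "that occurs during the DLT evaluation period (28 days of Cycle 1"). Note a in Appendix 1 places the DLT evaluation at the end of Cycle 1.
- **MTD analysis set, first sentence (11.2.2).** Treated subjects are included, except those with "missing data of one or more examination or observation items during the DLT evaluation period for other reasons than adverse drug reactions" (examples given: "worsening of clinical conditions due to progression of the primary disease, AEs for which a relationship with the study drug is ruled out") "and whose DLT evaluation could not be performed appropriately". Both conditions must hold for exclusion, and the second is not defined.
- **MTD analysis set, second sentence (11.2.2).** The set also takes in subjects with a Cycle 1 DLT, and "subjects who have received the study drug on at least 75% of the specified days in Cycle 1 in the absence of DLT".
- **Replacement (5.4).** Additional subjects are enrolled when someone "cannot be evaluated for DLTs because of withdrawal from the study before the end of Cycle 1 for any reason".
- **End of observation.** Follow-up is due 30 days (±5) after the last dose, but is moved ahead of any subsequent AML treatment (6.5). If follow-up becomes difficult after the last dose, for example through transfer or refusal to visit, "the study duration for the pertinent subject will be terminated on the relevant day" (6.1).
- **Details.** Section 11.2 defers the inclusion criteria for each set to a separately prepared SAP. The document reviewed contains no such separate text.

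**The concern.** Dosing comes early in each cycle, while the DLT window runs the full 28 days. Having taken 75% of the doses therefore does not show that the window was observed. The subject at issue is DLT-free, has passed the dosing threshold and leaves before Day 28 for a reason unrelated to the drug. In relapsed or refractory AML this is foreseeable: progression is the first withdrawal criterion in 5.6, and 11.2.2 itself names it as a cause of missing data.

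For this subject the two sentences of 11.2.2 can give opposite answers, and only the second has an objective threshold. If it is applied as written, the error has one direction. An early leaver with a DLT is counted as a DLT, and one without is counted as if seen for 28 days.

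The DLT data in this set inform the model recommendation, the overdose limit, the completion criteria and the MTD, which belongs to the primary objective. Cohorts are 3 to 6 subjects (3.2), so one classification can be a third of a cohort.

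**Working it through.** **1. Earliest day on which the threshold is met.** Doses needed = 0.75 × scheduled doses, rounded up. Schedules are from Sections 3 and 5.2.2.

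| Subtrial | Doses in Cycle 1 | 75% | Doses needed | Earliest day | Days of 28 left |
|---|---|---|---|---|---|
| A | 14 | 10.5 | 11 | 11 | 17 |
| B | 7 | 5.25 | 6 | 6 | 22 |
| C (Days 1–3, 15–17) | 6 | 4.5 | 5 | 16 | 12 |
| D | 21 | 15.75 | 16 | 16 | 12 |

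**2. The two sentences applied to one subject.** Suppose a Subtrial A subject takes 12 of 14 doses (86%), has no DLT, progresses and starts other AML treatment on Day 16.
- First sentence: data are missing for a non-drug reason, so the subject is excluded if the evaluation is judged inadequate, and 5.4 adds a subject.
- Second sentence: 86% is at least 75% and there is no DLT, so the subject is included.

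No text ranks the two sentences or sets a minimum observation time.

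**3. The plan's own figure.** Model (11.7.1): logit π(d) = log α + β log(d/160). Prior (11.7.2): (log α, log β) bivariate normal, means (−1.8999, 1.3484), SDs (2.2792, 1.3727), correlation −0.3157. Grid integration gives prior median DLT rates of 3.1% at 120 mg and 13.0% at 160 mg, matching the stated 3% and 13%.

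**4. Effect on a decision.** Data: 0/3 at 90 mg and 0/3 at 120 mg. At 160 mg there is one DLT, one fully observed non-DLT and one early leaver. Section 11.7.3 gives the 25% overdose limit without a direction; it is read here as below 25%. The limit applies from the third cohort, which the 160 mg cohort is.

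| Handling of the leaver | 160 mg data | P(DLT rate >33%) at 160 mg | 160 mg within limit? |
|---|---|---|---|
| Counted as non-DLT | 1/3 | 21% | Yes |
| Replaced, replacement has no DLT | 1/3 | 21% | Yes |
| Replaced, replacement has a DLT | 2/3 | about 60% | No |

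The model recommendation differs only in the last row, where it falls to 120 mg.

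**5. When observation really ends early.** For a leaver whose last dose falls at the threshold, the earliest default Follow-up is 25 days later: Day 36 in A (11 + 25), Day 31 in B (6 + 25) and Day 41 in C and D (16 + 25). All fall after Day 28. Truncation therefore needs early Follow-up before new AML treatment, transfer, refusal or death.

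**6. Direction and scale, under assumptions only.** Let p be the true 28-day rate, f the fraction leaving on day t with nothing seen afterwards, and q = 1 − (1 − p)^(t/28), a constant hazard. Take p = 0.33 and t = 11 (Subtrial A), so q = 0.146. The documents do not give f; 0.15 and 0.30 are assumed.
- Leavers without a DLT counted: (1 − f)p + fq = 0.302 and 0.275, so 33% appears as 30% and 27%.
- Leavers without a DLT dropped: [(1 − f)p + fq] / [(1 − f) + fq] = 0.302/0.872 = 0.347 and 0.275/0.744 = 0.369, so 33% appears as 35% and 37%.

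**The case against.** The strongest reply is that the plan already deals with early leavers. The first sentence of 11.2.2 is aimed at them and names progression, 5.4 adds subjects, and Appendix 1 puts DLT evaluation at the end of Cycle 1. This stands in part. A reader might infer from the second sentence alone that the plan has no rule for such subjects, and that would be wrong. But exclusion and replacement both turn on an undefined judgement, and the second sentence admits the subject without that judgement.

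Three stronger readings are tempting, and the documents do not support them.
- **That one early leaver by itself flips the 160 mg decision.** Comparing 1/3 (21%) with 1/2 (31%) suggests this. But 11.7.3 runs the model after evaluation in 3 subjects per cohort in principle, and 5.4 replaces the non-evaluable subject. The fair comparison is 1/3 against 1/3 or 2/3.
- **That a leaver fills one of the places needed to escalate.** Section 5.3.3 requires the end of the DLT evaluation period in at least 3 subjects and does not cite the 75% rule. The leaver fills a place only if that rule is read into 5.3.3.
- **That up to 30% leave early.** In U102, 26 of 37 subjects had a marrow assessment 28 days after the first dose. The other 11 (30%) lacked that assessment at a data cut-off in an ongoing study; this is not a count of departures.

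It is also true that default follow-up passes Day 28, that new AML treatment before Follow-up is discouraged (6.6), that dose decisions also use clinical and PK/PDy review, and that the separate SAP may settle precedence. These points limit the effect. They do not remove the conflict in the protocol text.

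**Conclusion.** The conflict is real and lies in the set used for the primary objective. For a DLT-free subject who passes 75% of dosing days and is truly unobserved before Day 28, 11.2.2 can point both ways and does not say which sentence governs. Read literally, the second sentence can only lower the estimated DLT rate.

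The effect on a decision is conditional. In the worked case the 160 mg dose stays within the limit at 21% unless the replacement has a DLT, which takes the probability to about 60%. This rests on the below-25% reading of 11.7.3 and on one data pattern.

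The size of any bias is unknown, because no Cycle 1 dropout rate is stated. The 30% to 27% range above is a what-if: every leaver goes at the earliest possible day, with no later observation. It should not be quoted as an estimate for this trial.

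**What to change.** Amend the second sentence of 11.2.2, and the SAP to match:
- A subject without a DLT is included only if dosed on at least 75% of the specified Cycle 1 days **and** observed for DLTs and safety through Day 28 without other AML treatment. Withdrawal and Follow-up assessments may supply that observation.
- Any other subject without a DLT is not evaluable and is replaced under 5.4.
- Every subject with a DLT is kept.
- This rule governs over the first sentence.
- The same definition applies wherever 5.3.2 and 5.3.3 refer to a completed DLT evaluation or the end of the evaluation period.

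The cost is some replacements and slower cohorts. There is also a modest conservative shift, because early DLTs are kept while early non-DLTs are dropped: under the assumptions in step 6, a true 33% would appear as 35% to 37% in Subtrial A. That should be acknowledged when the rule is adopted.

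Observation to Day 28 does not settle the hematological DLT in 5.3.1, which depends on a Cycle 2 delay of more than 2 weeks and so cannot be known by Day 28. Those passages need to be reconciled separately.
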